Statistical Analysis Plan (Addendum)

Increasing Knowledge of Alcohol as a Risk Factor for Breast Cancer Among Women Attending Breast Screening Services (Health4Her)

ClinicalTrials.gov Identifier: NCT04715516.

Pre-registered: Wednesday 20 January 2021

Version: 1

Date version finalised: Friday 18 February 2022

Study rationale and design

Alcohol is a major modifiable risk factor for breast cancer in women, yet this is not widely understood by health practitioners or policy makers, let alone the general population. We planned to undertake a pragmatic, single-site, double-blind, parallel group randomised controlled trial to test the effects of an alcohol brief intervention among women attending breast screening services, to improve knowledge of alcohol as a risk factor for breast cancer and reduce harmful alcohol use.

Women attending Maroondah BreastScreen for routine mammography (N = 558) completed a baseline assessment before being randomised to receive 4 minutes of alcohol brief intervention plus 3 minutes of lifestyle health promotion (active arm, n = 279), or 3 minutes of lifestyle health promotion, not inclusive of alcohol information (control arm, n = 279). For the active arm, participant responses to questions about current alcohol use branched to personalised feedback consistent with level of alcohol consumption (i.e. drinking within or above current Australian Alcohol Guidelines). Interventions were delivered by way of an animation on an iPad. Both groups also received take-home information pertaining to group assignment. Follow-up assessments were completed by telephone at 4- and 12-weeks post-randomisation.

Statistical Analysis Plan (SAP)

This plan, or SAP Addendum, provides additional detail to the statistical considerations that were documented in the statistical analysis plan in Health4Her Protocol_V7_08 08 21 (available in the trial record on ClinicalTrials.gov).

Data will be collated, cleaned and validated using programmed edit checks.

Outcomes with measurements at more than two time points

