In general, outcome variables with repeated measurements will be analysed by fitting linear mixed models (for continuous outcomes or outcomes treated as continuous, such as 5-point Likert scales) or (for categorical / binary outcomes) generalised linear mixed models (GLMMs) or generalised additive mixed models (GAMMs), with fixed effects for treatment and time, and their interaction, and random effects for subjects and assessments within subjects, using restricted maximum likelihood (REML) or similar algorithms. These models allow missing values to be accommodated.

These methods will allow the most suitable variance-covariance model for the repeated measures to be selected, using Akaike's Information Criterion, and, if appropriate, commonality of nonlinear trends over time to be explored via splines. The F-test (or equivalent chi square test, t-test of coefficients in logistic regression) will be used to test for an overall group by time interaction in outcomes measured at all three follow-up times (0, 4 and 12 weeks).

Outcomes measured at two or fewer time points

For outcome variables measured at two or fewer time-points, different models will be used, depending on the nature of the outcome variable:

- Where the outcome is binary and proportions are required, a test of change in proportions for categorical outcomes, e.g. the Cochran-Mantel-Haenszel test, will be applied or, if covariates are required in the analysis, logistic regression with random effects for subjects. Such logistic regression models are instances of GLMMs or GAMMs.
- 2. For continuous outcomes or outcomes treated as continuous (such as 5-point Likert scales) linear mixed models will be used (as for outcomes measured at three time-points).
- 3. In simple cases of the preceding points, the analysis may reduce to (in the sense of being equivalent to) a test of whether there is a difference between the two groups (treatment and control) in the changes in the mean (for continuous outcomes). If just one time point is involved, we may use a binomial test of proportions (for categorical outcomes).

Outcomes measured at 4 and 12 weeks but without a baseline measurement will be covered by this case.

Missing values

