Where possible, missing values will be handled under the missing at random assumption; that is, unless there is good reason to believe this assumption is untenable. In cases of doubt the analysis will be re-done with (a) missing values imputed and (b) the corresponding subjects removed from the analysis.

Outcomes where there is no baseline measure possible (that is, by design) will not be treated as having the baseline value missing, but rather as belonging to the two time-point case.

Exploratory analyses

Exploratory analyses will be performed using the same methods as for the primary and secondary outcomes (as appropriate) plus, optionally, such other modelling strategies as may be useful (e.g. random forests or decision trees as exploratory tools, or other classification tools).

In exploratory analyses of outcomes measured at three time-points, mixed models with covariates as relevant (see list of potential covariates below), including their interactions with treatment group, will be fitted in order to identify moderating factors. Categorical, ordinal and binary outcomes will be analysed in a similar way using generalised linear mixed models (GLMMs) or generalised additive mixed models (GAMMs).

In exploratory analyses of outcomes measured at two time-points, logistic regression with random effects for subjects will be utilised to assess the effects of potential covariates (see list of potential covariates below).

Statistical software

Analyses will be conducted using the most appropriate procedures in GenStat, R, SAS or STATA and additional analyses not specified in the published protocol or this addendum will be regarded as exploratory.

Statistical Analysis of the Primary and Key Secondary Outcome Variables

Primary Outcome

The primary analysis will take place after all subjects, not known to have withdrawn or not deemed lost to follow-up, have had their 12-week assessments, based on the intention to treat (ITT) principle (i.e. subjects' data are analysed as randomised and as stratified).

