The primary outcome of this repeated measures RCT is the proportion of participants accurately identifying alcohol as a clear risk factor for breast cancer at 4-weeks post-randomisation. Inferences about the effect of the Health4Her intervention on the primary outcome will be based on a comparison, between treatment groups, of change from baseline to 4-weeks post-randomisation using a Cochran-Mantel-Haenszel test. This analysis tests for homogeneity of the odds ratio across strata (i.e. intervention and control). A binomial test (that is, a test of proportions) will be used as an ancillary analysis of the primary outcome (i.e. the difference in proportions between the two groups at 4-weeks post-randomisation).

Relevant covariates (from the list of potential covariates below) may also be used in further analysis, using generalised linear models (logistic regression) to make comparisons. Additional analyses may use covariates for post-stratification.

Secondary Outcomes

Alcohol Consumption

Alcohol consumption will be assessed by the Alcohol 14-day Timeline Follow-back (TLFB). Heavy drinking days are measured as >40 grams of alcohol (>4 Australian standard drinks). Alcohol consumption will also assessed by the AIHW alcohol frequency quantity items. Assessments are made at 0, 4 and 12 weeks and linear mixed models (continuous variables) or GLMMs or GAMMs (categorical / binary variables) will be used. The following outcomes will be analysed (transformed if necessary for analysis):

Secondary outcome 1 – Proportion of participants drinking less than or equal to 10 standard drinks per week at 4-weeks and 12-weeks post-randomisation. Derived from (operationalised in two ways):

- Has the participant consumed >10 standard drinks in week one AND/OR >10 standard drinks in week two? (tlfb_nhmrc_both_comprh)
- Has the participant consumed >10 standard drinks in both week one AND week two? (derived variable: tlfb_nhmrc_bothwks)

Secondary outcome 2 – Proportion of participants drinking less than or equal to 10 standard drinks per week at 4-weeks and 12-weeks post-randomisation, among only participants who drink more than 10 standard drinks per week at baseline.

Subgroup defined as either i. women who consumed >10 standard drinks in week one AND/OR >10 standard drinks in week two (tlfb_nhmrc_both_comprh) or ii. women who consumed >10 standard drinks in both week one AND week two (tlfb_nhmrc_bothwks).

Outcome derived from:

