 - derived from atttd_changerisk
 - Likert response

Potential covariates for exploratory analyses of primary and secondary outcomes

- age (continuous; categorical 40-49, 50-59, 60-69, 70+ years)
- lgbtq+
- education
- born in Australia
- culturally and linguistically diverse background
- household composition
- disability status
- alcohol consumption at baseline (drinking above/within current NHMRC guidelines, 14-day TLFB subscales scores, AIHW frequency quantity scores)
- QoL/health-related QoL at baseline (SF-12 mental and physical component scores, EUROHIS-QOL single item)
- health literacy at baseline (attitude and knowledge scores)

ⁱGraeme Tucker, Robert Adams, David Wilson. New Australian population scoring coefficients for the old version of the SF-36 and SF-12 health status questionnaires, Qual Life Res (2010) 19:1069-1076, DO 10.1007/s11136-010-9658-9

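### Exploratory moderator models for outcomes at 0, 4 and 12 weeks name only covariate-by-treatment terms; read literally, these average in pre-randomisation week 0 and estimate about two-thirds of the true moderation

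*SAP*

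**What the plan says.** The SAP section on exploratory analyses sets out the moderator models: "In exploratory analyses of outcomes measured at three time-points, mixed models with covariates as relevant", and these covariates, "including their interactions with treatment group, will be fitted in order to identify moderating factors". Time does not appear in that description of the interactions.

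Three other places fix what such a model contains.

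- **Base model** (SAP, outcomes with measurements at more than two time points): mixed models "with fixed effects for treatment and time, and their interaction, and random effects for subjects and assessments within subjects". The treatment effect is judged by a "test for an overall group by time interaction in outcomes measured at all three follow-up times (0, 4 and 12 weeks").
- **Visits** (SAP, alcohol consumption outcomes): "Assessments are made at 0, 4 and 12 weeks and linear mixed models (continuous variables) or GLMMs or GAMMs". Week 0 is therefore one of the responses.
- **Timing of week 0** (SAP, study rationale and design): women "completed a baseline assessment before being randomised to receive 4 minutes of alcohol brief intervention" or the control material, so week 0 is before treatment.

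The SAP's list of potential covariates includes "alcohol consumption at baseline (drinking above/within current NHMRC guidelines, 14-day TLFB subscales scores, AIHW frequency quantity scores"). Some candidate moderators are thus the week-0 values of the outcomes being modelled.

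**The concern.** In a model with week 0 among the responses, the arms differ at week 0 only by chance, and the intervention shows itself as a change in the arm difference after week 0. That is why the SAP tests group by time. A covariate that moderates this effect does so through covariate by treatment by time. A covariate by treatment term with no time component measures something else: how the arm difference, averaged over weeks 0, 4 and 12, varies with the covariate. One of those three visits cannot carry a treatment effect.

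These analyses are meant to indicate for whom the intervention works. Protocol section 14.1 says this pilot will inform a later multicentre trial, so an understated moderator, or a chance baseline difference read as moderation, could mislead the choice of whom to target.

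**Working it through.** **The plan's own figure.** The documents give no power, effect size or within-woman correlation for moderator analyses. The only design figure is the sample size in protocol section 14.1, which reproduces. With rates 0.22 and 0.34 (mean 0.28), two-sided alpha 0.05 and 80% power:

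n per arm = [1.960 × √(2 × 0.28 × 0.72) + 0.842 × √(0.22 × 0.78 + 0.34 × 0.66)]² / 0.12² = 218.6, rounded up to 219.

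Allowing for 20% attrition, 219 / 0.8 = 273.75, so 274 per arm and 548 in total. The moderator question does not bear on this figure.

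**Assumptions for the moderator term.** Continuous outcome, variance 1 at each visit, correlation r between any two visits (compound symmetry), complete data, and true moderation of 0 at week 0 and d at weeks 4 and 12. The documents give no r, so a range is shown.

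**Estimate.** The time-constant covariate by treatment term targets the average over visits: (0 + d + d) / 3 = 0.67d. Under first-order autoregressive correlation it is 0.52d to 0.64d (r from 0.9 down to 0.2). In a simulation with N = 558 and an assumed 20% missing at each follow-up it was 0.59d to 0.62d.

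**Power, moderator other than the outcome's own baseline.**

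- Two-way term: signal 2d/3, variance proportional to (1 + 2r)/3.
- Pooled change contrast, mean of weeks 4 and 12 minus week 0: signal d, variance proportional to (1 + r)/2 + 1 − 2r = 1.5(1 − r).
- Relative efficiency E = [(4/9) / ((1 + 2r)/3)] × 1.5(1 − r) = 2(1 − r)/(1 + 2r).
- Where the pooled contrast has 80% power its expected z is 1.960 + 0.842 = 2.802. The two-way term has expected z of 2.802 × √E.

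| r | E | Two-way power when the pooled contrast has 80% |
|---|---|---|
| 0.2 | 1.14 | 85% |
| 0.25 | 1.00 | 80% |
| 0.3 | 0.88 | 75% |
| 0.4 | 0.67 | 63% |
| 0.5 | 0.50 | 51% |
| 0.6 | 0.36 | 39% |
| 0.7 | 0.25 | 29% |
| 0.8 | 0.15 | 20% |

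The simulation with missing data, two-way against pooled contrast, gave 69% v 82% at r = 0.3, 50% v 81% at 0.5, 26% v 82% at 0.7 and 17% v 77% at 0.8.

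**Moderator that is the outcome's own continuous baseline.** The week-0 response equals the covariate, so its slope on the covariate is 1 in both arms and the week-0 interaction is exactly zero, without noise. The two-way term is then 2/3 of the mean interaction at weeks 4 and 12, and its standard error shrinks by the same 2/3. The test statistic does not change. A simulation (N = 446, complete data, 120 runs per value of r) compared it with baseline by treatment on weeks 4 and 12 only. Mean z was 2.82 v 2.82 at r = 0.4, 2.81 v 2.81 at 0.6 and 2.84 v 2.84 at 0.8.

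**If all three-way terms are fitted.** With week 0 as the reference visit, the covariate by treatment coefficient is the week-0 difference alone. It contains no treatment effect, so naming that term would still point to the wrong coefficient.

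**The case against.** The strongest reply is that the SAP does not commit to a time-constant two-way test. The exploratory section opens by carrying over the methods of the primary and secondary outcomes where appropriate. For three-visit outcomes that method is judged by group by time. A statistician could reasonably take covariate interactions with treatment to include their interaction with treatment by time, and nothing excludes it. This stands: a reader might infer that the SAP prescribes the wrong test, but the documents show only that the one interaction named is not the one needed. It does not remove the point, because the sentence that defines the moderator models names only that interaction and the two candidate terms answer different questions.

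Three further replies also stand in part.

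- A reader might infer that most real moderation would be missed. The documents give no correlation, and that reading needs r above about 0.5. At 0.25 the two tests are equal, and below that the two-way test has more power.
- A reader might take heavier against lighter drinkers as the worst case. If baseline consumption enters as the continuous week-0 value of the same outcome, power is unchanged and chance baseline imbalance cannot enter; only the coefficient is too small. This exact result does not extend to a dichotomised baseline. Women above 10 drinks per week are also analysed directly in secondary outcomes 2 and 4, although those subgroup analyses are not interaction tests.
- The 80% benchmark is a pooled one-degree-of-freedom contrast. At the same effect, a joint two-degree-of-freedom test of weeks 4 and 12 has 71% power and a single-visit contrast 68%. The gain depends on making the pooled contrast the one that is judged.

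**Conclusion.** The point holds as a fault in an exploratory specification. Followed literally, the named term estimates about two-thirds of the true moderation under equal moderation at weeks 4 and 12, compound symmetry and complete data, and somewhat less under autoregressive correlation or with missing follow-ups. This dilution is present at every correlation examined.

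The loss of power is conditional. For moderators other than the outcome's own continuous baseline, it runs from 80% to 75% at an assumed r of 0.3, and from 80% to 20% at 0.8, with no loss at or below 0.25. For these moderators a chance baseline imbalance by covariate can also enter the estimate. The figures are for continuous outcomes and should not be carried over unchanged to the binary outcomes fitted by GLMM or GAMM.

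A reader might infer that the trial's main conclusions are at risk. They are not: the primary analysis, the secondary-outcome tests and the sample size do not use these models.

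**What to change.** Replace the moderator sentence in the SAP's exploratory section with wording to this effect:

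> For outcomes at 0, 4 and 12 weeks, covariate by time, covariate by treatment and covariate by treatment by time will be added to the model. Moderation will be judged from covariate by treatment by time, using the pooled post-baseline contrast (weeks 4 and 12 against week 0); the separate week 4 and week 12 contrasts will be reported. Where the moderator is the outcome's own baseline value, weeks 4 and 12 will be the responses, baseline will be a covariate, and baseline by treatment will be the moderation term.

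This needs no new data. The downside is a few more parameters in each exploratory model and, where r is below about 0.25, somewhat less power than the two-way term, in exchange for an estimate of the intended quantity.

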##### Feb 2021 – Nov 2021

**Implement intervention:** recruit 248 participants over 7 months, consent, baseline assessment, deliver alcohol brief intervention (or control), 4-week and 12-week follow-up telephone assessments, data entry.

**(Aug 2021)** Last participant recruited

**(Nov 2021)** Last 12-week follow-up assessment completed

**(Feb - Nov 2021)** Process and impact program evaluation

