### 3 STUDY OBJECTIVES

#### 3.1 Primary aim and hypothesis

***At 4-weeks post-randomisation, proportion of participants in the active condition (relative to control) accurately identifying alcohol as a clear risk factor for breast cancer.***

We hypothesise that at 4-weeks post-randomisation, compared to the control group, a greater proportion of participants receiving alcohol brief intervention will be able to accurately identify alcohol as a clear risk factor for breast cancer.

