## 14 STATISTICAL METHODS

### 14.1 Sample Size Estimation

Since the aims of this pilot RCT include preliminary hypothesis testing for effectiveness, a power and sample size calculation has been performed (Moore, Carter et al. 2011). Power and sample size estimates were carried out using PS: Power and Sample Size Calculation V3.1.2 (Dupont and Plummer 1990), assuming a type 1 error probability of  $\alpha < 0.05$ , 2-tailed, and equal-sized groups. Power calculations are based on the primary endpoint, proportion of participants who accurately identify alcohol as a clear risk factor for breast cancer.

Our sample size estimation is based on our previous online survey study with 391 women who have attended/are eligible to attend breast screening services (Health4Her Phase I). If the proportion of control participants who accurately identify alcohol as a clear risk factor for breast cancer is 0.22 and the true response rate for participants receiving the alcohol brief intervention is 12% greater at 0.34, and compensating for 20% attrition at follow-up, then 548 participants (274 per arm) will provide power of 80% to be able to reject the null hypothesis.

Given the lack of definitive evidence regarding alcohol BI effects in women, and particularly women of middle- and older-age in a breast screening setting, this powered pilot RCT will inform the development of a subsequent, comprehensive multicentre trial. This pilot RCT will generate preliminary data on intervention response using exploratory surrogate/proximal markers of effectiveness (e.g. proportion of participants accurately identifying alcohol as a breast cancer risk factor, proportion of participants drinking within guidelines, alcohol consumption and well-being), and will provide concrete estimates of risky alcohol consumption prevalence, and expected rates of missing data and participant attrition specific to the population under study (Moore, Carter et al. 2011).

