### 14.2 Statistical Analysis Plan

A detailed statistical analysis plan will describe the statistical methods for each outcome as well as how missing data will be dealt with. Data will be collated, cleaned and validated, using programmed edit checks, in a database that will be locked prior to analyses. All statistical tests will be two-tailed, with alpha level set to 0.05. Statistical analyses will be adjusted for multiple comparisons when indicated. 95% confidence intervals will be reported throughout. All randomised participants will be included in the analysis (i.e. intention-to-treat) for primary and secondary outcomes. Demographic characteristics (e.g. age) and baseline measurements (e.g. knowledge of alcohol as a clear risk factor for breast cancer, alcohol consumption) will be summarised and reported by intervention arm. The analyses will examine change in outcomes over time (4-weeks and/or 12-weeks) relative to baseline. The complete details of the analyses will be specified in a Statistical Analysis Plan that will be reviewed and approved by a study team prior to database lock. Analyses will be conducted using the most appropriate procedures in R and STATA.

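### The primary test is named as Cochran-Mantel-Haenszel but described as a homogeneity test, and neither is the comparison behind the 80% power

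*SAP*

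**What the plan says.** **SAP, Primary Outcome.** The outcome is the proportion of women who identify alcohol as a clear risk factor for breast cancer at 4 weeks. Inference "will be based on a comparison, between treatment groups, of change from baseline to 4-weeks post-randomisation using a Cochran-Mantel-Haenszel test". The next sentence explains the test: "This analysis tests for homogeneity of the odds ratio across strata (i.e. intervention and control". The direct comparison of the arms at 4 weeks is kept in a lesser role: "A binomial test (that is, a test of proportions) will be used as an ancillary analysis of the primary outcome".

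**SAP, Outcomes measured at two or fewer time points.** CMH is offered for binary outcomes as a test of change in proportions. A model that links a woman's two answers appears only as an option: "if covariates are required in the analysis, logistic regression with random effects for subjects". Secondary outcome 6 uses the same CMH wording as the primary outcome.

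**Protocol.** Section 3.1 hypothesises that, "compared to the control group, a greater proportion of participants receiving alcohol brief intervention will be able to accurately identify alcohol". Section 14.1 assumes 0.22 versus 0.34, two-tailed 5% and 20% attrition, and concludes: "then 548 participants (274 per arm) will provide power of 80% to be able to reject the null hypothesis". Section 14.2 says: "The analyses will examine change in outcomes over time (4-weeks and/or 12-weeks) relative to baseline". It names no primary test.

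**The concern.** The named test and the stated null hypothesis belong to different procedures. CMH takes the odds ratio as common to all strata and asks whether it equals 1. Asking whether the odds ratio differs between strata needs a homogeneity test (Breslow-Day, Woolf) or an arm-by-time interaction, and the SAP names neither for this outcome. Its group-by-time test covers only outcomes measured at 0, 4 and 12 weeks.

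With the arms as strata, the table inside each stratum is time by response. CMH then tests for a time effect shared by both arms, with arm conditioned out.

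The comparison-of-change wording, and Protocol 14.2, suggest that an arm-by-time comparison was meant. That is a legitimate target, but pairing and scale are left open, so two competent analysts could run different primary tests and both claim to follow the plan. None of these tests is the one that the sample size supports, and the SAP gives the primary test precedence over the ancillary one if they disagree.

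**Working it through.** **Inputs.** From Protocol 14.1 and 14.2: control 0.22, active 0.34, two-sided 5%, equal arms, 20% attrition, 274 per arm. Assumed, because the documents do not give them: baseline proportion 0.22 in both arms, and within-woman correlation ρ of 0, 0.3, 0.5, 0.6 or 0.7, equal in both arms.

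**1. Reproduce the plan's figure.** Two-proportion formula with pooled variance under the null, mean proportion 0.28:

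n = [1.96 × √(2 × 0.28 × 0.72) + 0.8416 × √(0.22 × 0.78 + 0.34 × 0.66)]² / 0.12² = 218.6, so 219 per arm.

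219 / 0.8 = 273.75, so 274 per arm and 548 in total, an exact match. The continuity-corrected version gives 588 and the one-sided version 434. The protocol does not name the test behind its power, so this is inferred from the match.

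**2. Power of each candidate test.** 219 completers per arm (274 × 0.8), 40,000 simulated trials per row, control staying at 0.22 and active reaching 0.34 at 4 weeks. Power (%) by ρ:

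| Test | 0 | 0.3 | 0.5 | 0.6 | 0.7 |
|---|---|---|---|---|---|
| Odds-ratio homogeneity across arms, visits treated as independent (Woolf) | 47 | 47 | 47 | 46 | 45 |
| Odds-ratio homogeneity, paired (log ratio of discordant pairs) | 46 | 62 | 76 | 86 | 96 |
| Difference between arms in paired change (risk difference) | 54 | 70 | 83 | 91 | 97 |
| Two proportions at 4 weeks | 80 | 80 | 80 | 80 | 80 |
| CMH of arm by 4-week response, stratified by baseline response | 80 | 84 | 90 | 94 | 98 |

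The paired odds-ratio test has 80.8% power at ρ = 0.55; the paired risk-difference test has 79.5% at ρ = 0.45.

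*Hand check, paired risk difference at ρ = 0.5.* The variance of one woman's change is p₀q₀ + p₁q₁ − 2ρ√(p₀q₀p₁q₁).
- Control: 0.1716 + 0.1716 − 0.1716 = 0.1716.
- Active: 0.1716 + 0.2244 − 0.1962 = 0.1998.
- SE = √(0.3714 / 219) = 0.0412; 0.12 / 0.0412 = 2.91; power = Φ(2.91 − 1.96) = 83%.

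*Hand check, independent visits.* The log odds ratio for active is ln[(0.34/0.66) / (0.22/0.78)] = 0.602, and for control 0.
- SE = √[3 / (219 × 0.1716) + 1 / (219 × 0.2244)] = 0.317; 0.602 / 0.317 = 1.90.
- The expected statistic lies just below 1.96, so power stays just under one half whatever the correlation.

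**3. Type I error.** With both arms at 0.22, 0.25, 0.28 or 0.30 at 4 weeks, every test in the table rejects in at most 5.3% of trials. The independent-visit version becomes very conservative: 4.8%, 1.8%, 0.6%, 0.2% and 0.0% across the five correlations when both arms rise to 0.30.

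**4. Disagreement under the planned effect.** The ancillary test is significant and the paired odds-ratio test is not in 36%, 25%, 15%, 8% and 3% of trials; the reverse occurs in 2%, 6%, 10%, 14% and 18%. With the independent-visit version as primary, the figures are 35–40% and 2–6%.

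**5. The literal test: CMH of time by response, stratified by arm.** When both arms rise equally from 0.22 to 0.30, so that the intervention has no effect, it rejects in 77%, 81%, 85%, 88% and 92% of trials. Under the planned effect it rejects in 54–57%. With a true 12-point difference made of opposite movements (0.16 versus 0.28, from 0.22), it rejects in only 0.5–5% (ρ from 0.5 to 0, 20,000 trials per row).

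**The case against.** The strongest reply is that the SAP states its target twice and consistently: a between-group comparison of change, and homogeneity across the arms. Both describe an arm-by-time contrast, Protocol 14.2 supports it, and only the label is wrong. On that view the rejection rates of 77–92% belong to a reading nobody would adopt, and the power argument has no fixed direction because it turns on an undocumented correlation. Much of this is fair. The literal reading is the less likely one, and a paired comparison of change can exceed 80% power.

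The crossing points near 0.55 and 0.45 also depend on equal correlation in both arms. With 0.6 in control and 0.3 in active, paired odds-ratio power is 48% and risk-difference power 79%; with 0.7 and 0.4, they are 51% and 86%. At ρ = 0.7 the active arm's correct-to-incorrect cell expects only 1.7 women, so the 96% is fragile. These points limit the precision of the thresholds. They leave intact the conclusion that power may lie on either side of 80%.

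Correcting the label alone would still leave pairing and scale undefined for the one test that carries the inference.

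A further objection is that baseline-stratified CMH changes the analysis when a paired arm-by-time test would do. That test would indeed cure the contradiction. It would not match the stated power unless the correlation is high enough. Finally, the SAP wants analysis to respect the randomisation strata. Protocol section 6 mentions strata without defining them, and nothing in the proposed test conflicts with them.

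**Conclusion.** The concern holds. The primary test is wrong as written, because CMH with the arms as strata does not test what the SAP says it tests. The likely intent is valid and protects type I error, but it is not defined well enough to run.

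The 80% power belongs to the ancillary two-proportion test. For the intended comparison, power against the planned effect runs from about 45% to 97%, depending on pairing, scale and correlation. These figures assume 219 completers per arm, a baseline of 0.22 in both arms and equal correlation across arms. Using the 558 women actually randomised changes little: 279 × 0.8 gives 223 per arm and 80.8% power for the two-proportion test. The finding is not that the trial is underpowered. It is that the primary test is undefined and detached from its sample-size basis.

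**What to change.** Issue a dated SAP amendment that states whether anyone had seen outcome data by arm. In it:

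- Delete the sentence on homogeneity of the odds ratio.
- Define the primary analysis as a CMH test of arm by 4-week response, two-sided 5%, without continuity correction, with baseline response (yes/no) as the strata. Report the Mantel-Haenszel common odds ratio and risk difference with 95% confidence intervals.
- Keep the two-proportion test at 4 weeks as ancillary.
- Use the same wording for secondary outcome 6.

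This keeps the named method, uses each woman's baseline answer, addresses the hypothesis in Protocol 3.1 and holds type I error at about 5%. Its power is at least 80% at every correlation tried, and 88–92% in the two unequal-correlation cases. If the team prefers a comparison of change, a paired arm-by-time test with a stated scale is acceptable, but the 80% power should then not be claimed for it without a stated correlation.

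The cost in data and code is one paragraph and no new data. The real cost is timing. The Protocol timeline gives November 2021 for "Last 12-week follow-up assessment completed", and the SAP was finalised on 18 February 2022. Changing the stated primary test after those dates must be justified and disclosed in the report.
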